Study procedures. Study procedures are illustrated in Figure 2 (below). Participants who meet screening criteria and would like to be part of the study will go through an informed consent process, described above. Following consent procedures, participants will complete the baseline assessment. When the baseline assessment is finished, all eligible participants will receive a wireless adherence monitoring device, also known as Wisepill. Participants will then use the device for two weeks to enable two weeks of wireless medication monitoring as a baseline assessment of ART adherence. Approximately two weeks after the baseline

assessment, participants will be invited to come back to the clinic for randomization. Participants will be randomized into either 1) the intervention group (the paraprofessional adapted intervention to improve ART adherence and substance use) or 2) the control group (the enhanced standard of care). Randomization assignment will not affect patients' use of other ART clinic services. Regardless of condition, participants who attend all mandatory visits (intervention: all assessments and all six intervention sessions; control: all assessments and midpoint urinalysis) will receive a completion certificate at the end of their final assessment (six-month follow-up assessment).

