Assessment visits. All participants will first attend a baseline assessment where they will begin monitoring their ART medications with Wisepill. Approximately two weeks later, participants will return to the clinic to undergo randomization. Those randomized into the intervention group will receive their first intervention visit, and have a total of six intervention sessions over a total of eight weeks. Those randomized into the control condition will receive an enhanced standard of care, described below. Approximately 3 months after the baseline assessment (and directly after intervention group members' last intervention visit), participants will come back to the clinic for a post-treatment assessment. They will return the Wisepill device at this assessment. Approximately 3 months after this assessment (6 months after baseline), participants will come in again for a final post-treatment assessment (6-month follow-up). Both post-treatment assessments will contain the same psychosocial self-report questionnaires as the baseline assessment (with exception of the demographic questionnaire) and the same biological assessments. Assessments and participant tracking will be done by bilingual research assistants. Participants will receive modest reimbursements for the follow-up assessments (150 Rand grocery voucher), and a 50 Rand reimbursement for local travel expenses to the study clinic will be provided for all non-major assessment visits.

When it is medically appropriate, the study will obtain permission from the participants to communicate their CD4 and viral load results and/or their struggles with substance use to their medical provider. This will only be done on a case-by-case basis, when, for example, study staff are aware that the clinic does not have the latest blood results of the participant or the participant needs more help with substance use than our study can offer. The study will only release this information with participants' permission, asking them to sign a medical release form. With this information, their provider can then make informed treatment decisions.

Figure 2: Study Design

Control Group (Enhanced Standard of Care). The control group will receive an enhanced standard of care (ESOC), which is a referral to a local substance use treatment clinic (there is a co-located Matrix^{47,48} program at the recruitment site, which is an evidence-based 16-

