the participant's substance use and medication adherence, reviewing behavioral activation from the previous week, including continuing to identify health, substance-free rewarding activities in the patient's life. Next, basic skills of mindfulness-based relapse prevention will be introduced (i.e., increase one's awareness of how craving feels in one's body, strategies for slowing down and not acting on urges/cravings, and coping with and responding to cravings in the moment). The session will end with a mindfulness exercise and participants are encouraged to schedule healthy, substance-free activities in between sessions.

- Session 4: Mindfulness-based relapse prevention (MBRP). The focus of Session 4 will be MBRP. In this session, the interventionist and participant will check in about the participant's substance use and medication adherence in the past week, review content from past sessions, and continue to build upon prior week's introduction to mindfulness-based relapse prevention strategies. This session will also end with a mindfulness exercise, which participants are encouraged to practice between sessions.
- Sessions 5 & 6: Relapse prevention continued. Sessions 5 and 6 will focus on reviewing the material learned in previous sessions and working more on relapse prevention. The interventionist and participant will check in about the participant's substance use and medication adherence in the previous week, review items learned in previous sessions, and plan ahead to prevent future relapse. Both sessions will end with a mindfulness exercise.
- Optional Booster Sessions: After completing the 6 intervention sessions, participants will be allowed to attend up to 6 booster sessions. These sessions must be completed after the 6th intervention session and before the six-month follow-up assessment. Booster sessions will consist of topics and skills from the previous 6 sessions to address any difficulties with adherence and/or substance use. The purpose of the booster sessions is to help those who may need additional time to reinforce the strategies of the intervention.

While it is preferred for intervention sessions to be done in person at the clinic, intervention participants who are unable to go to the clinic will have the option of telephone sessions. Allowing interventions over the phone will make the intervention accessible to participants who have difficulty traveling to the clinic or who may be traveling.

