1. CD4 count and Viral Load: CD4 count and viral load will be extracted from participants' medical record at each major visit. If results are not available within 3 months of the baseline assessment and 30 days of the follow-up assessments (post-treatment assessment and 6-month follow-up assessment), participants will be invited to undergo a blood draw. These procedures will not add any cost to the patient. CD4 count will be used as a measure of immune function and disease progression. Viral load will be used as a biological indicator of ART adherence. Viral load will also be used to document the percentage of the sample with virological suppression (measured dichotomously at < 400 copies/mL).
2. Dried Blood Spot (DBS): We will be collecting and storing dried blood spots. Analysis by DBS will allow for a gross confirmation that at least some recent ART is present in the system.⁷⁹ This biological confirmation will be used as verification of Wisepill data. One vial of blood for DBS will be taken at each major assessment. In addition to adherence, we are storing DBS for future biomarkers in our freezer. We will ship and then destroy samples before five years after the study is completed.
3. Urinalysis. Urinalysis will be used as a biological indicator of alcohol and drug use. Urinalysis will be conducted at all major assessments (baseline, post-treatment assessment, 6-months follow-up assessment) and at intervention participants' third session (halfway through the intervention) by a trained research assistant using rapid detect urine tests. Control participants will also be asked to come into the clinic for urinalysis between their baseline and post-treatment assessment (approximately 5-weeks post-randomization). These urine tests detect cocaine, marijuana, amphetamines, opiates, phencyclidine and alcohol, and give dichotomous results. Since there is potential stigma related to substance use, and participants may falsely believe that ART will be withheld in the context of use,⁶⁶ study procedures include dialogue with the participant to ensuring anonymity of the results.

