For those in the integrated treatment condition, interventionists will be free to deviate from the protocol to ensure participant safety. Referrals will be made for a higher level of care if at any point symptoms worsen and are no longer manageable with the integrated treatment alone, or if withdrawal symptoms require medical attention. For those in the control condition, if there are increases in severity of substance use and/or signs of potentially medically dangerous withdrawal symptoms at study visits, the independent assessor will make appropriate referrals for next-level of care. In addition, Drs. [name] and [name] are clinical psychologists with specializations in addiction and mental health concerns, respectively. They will be contactable by cell phone in the case of emergency to provide supervision if required. Further, there are community health psychologists and psychiatrists in the clinic where recruitment will occur who will be available in the case of emergency. In the event that a higher level of substance use treatment is required, there are substance use treatment clinics that

regularly receive referrals from the clinic site where recruitment will occur (i.e., Matrix), and there are existing protocols in place for making this referral. If an inpatient level of care or emergency services is required for management of withdrawal symptoms, treatment is available at either of two local area hospitals in Cape Town, a short distance from both clinic sites: G.F. Jooste Hospital and Karl Bremer Hospital. In the event that study participants need this level of care, transport will be arranged for them in-line with clinic protocols either through the Health Transport System NetCare or by ambulance. Referral options may also include referral to mental health and social sector services. Study procedures do not preclude participant referral for additional care and treatment and in each case where additional levels of care are required, decisions regarding the participant's continuation in the study will be based solely on a consideration of the participants' welfare. In both conditions, referrals for substance use treatment and/or a higher level care will also be made at the end of the study period if severe symptoms are present.

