For the purposes of this study, all SAEs will be required to be reported to the Committee, regardless of any judgment of their relatedness to the study. All relevant information will be reported to the DSMB for each SAE including information about the event and its outcome, study condition, concomitant medications, the subject’s medical history and current conditions, and all relevant laboratory data. This will be provided annually at the DSMB committee meeting.

Reporting to site-specific IRBs will be done within 24 hours of the study team being made aware of the SAE. Reporting of any study-related SAEs and SAEs that severely impact participants (i.e., participant deaths) will be made to NIDA within 24-72 hours of the study team being made aware of the SAE.

Non-Serious Adverse Events. At yearly intervals during the course of the study and then again at its completion, the DSMB will be provided with unblinded summaries of the numbers and rates of adverse events by treatment group. These reports will include types of events, severity, and treatment phase. Data on individual non-serious adverse events is not expected to be needed for this review.

Other Safety-Related Reports. At yearly intervals throughout the course of the study, the DSMB will also receive unblinded summary reports of treatment retention and reasons for dropout, by treatment arm and study phase.

Trial Efficacy

Plans for interim analysis for efficacy data.

If at any time during the course of the study, the Committee judges that risk to subjects outweighs the potential benefits or a safety concern arises, the Committee shall have the discretion and responsibility to recommend that the study be terminated. However, there are no pre-specified interim analysis for efficacy data given that (1) this is not an efficacy trial, rather a hybrid effectiveness-implementation trial; (2) the low anticipated risk of participation in the behavioral intervention and (3) small sample size. The power analysis is such that the full N would be required to make this determination. However, the DSMB will have the power to request analyses should they deem it necessary.

DSM Plan Administration

Responsibility for data safety and monitoring.

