Measure	Screening	Baseline	Post-Treatment	6- Month Follow-Up
Demographics		X		
Mode of HIV Infection		X		
AUDIT		X	X	X
WHO-ASSIST	X		X	X
Substance Use History Questionnaire		X	X	X
Economics & RUQ		X	X	X
Sexual Risk-Taking Questions		X	X	X
ACTG- SF-21		X	X	X
Barriers to Adherence		X	X	X
Robbed, Recreational ARVs		X	X	X
Brief RCope		X	X	X
PHQ-9		X	X	X
PTQ		X	X	X
BADS		X	X	X
RPI		X	X	X
SOCRATES		X	X	X
SIP		X	X	X

PACS		X	X	X
Interactive Toxicity Beliefs Questionnaire		X	X	X
Ira Wilson's Three-Item Self-Report Measure		X	X	X
Substance Use and HIV Related Stigma Scale (SU and HIV- SMS)		X	X	X
Acceptability/Feasibility Questionnaire			X	X
Urinalysis		X	X	X
Blood Draw (DBS; CD4 count and viral load – when results not available in clinic records in past 3 months for baseline/ 30 days for follow-ups)		X	X	X
Chart Extraction		X	X	X
Wisepill		X	X	
Timeline Follow-Back		X	X	X
Exit Interview (subset of intervention participants)				X

Table 2. List of Measures During Intervention
(Participants randomized to intervention condition only)

Measure	S1	S2	S3	S4	S5	S6
SRA Weekly Adherence	X	X	X	X	X	X
Wisepill	X	X	X	X	X	X
Timeline Followback*	X*	X	X*	X	X	X
Urinalysis*			X*			

*Control participants will also be invited to the clinic for urinalysis and timeline follow-back approximately 5-weeks post-randomization (approximately equivalent in time to Session 3). Control participants will also do timeline follow-back at their randomization visit (corresponding to intervention participants' Session 1).

REFERENCES

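### Adverse events are recorded as staff become aware of them, and the intervention arm has about twice the scheduled visits, so the by-arm adverse event rates sent to the DSMB may lean toward apparent excess in that arm

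*Protocol*

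**What the plan says.** Protocol section F (Data safety and monitoring plan, Non-Serious Adverse Events) says that each year and at completion "the DSMB will be provided with unblinded summaries of the numbers and rates of adverse events by treatment group". The summaries are split by event type, severity and treatment phase. Section F also has each AE classed by its likely relation to the intervention. An AE is any harmful occurrence, whether or not study-related, and mild events count.

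On how events are found, section F (Responsibility for data safety and monitoring) says only that staff who learn of an AE report it to the principal investigator and site project director. Neither table in the List of Measures contains an AE inquiry, and the SAP does not mention AEs. For controls, section B of the ethics chapter (Worsening symptoms) ties detection to visits: referral follows "if there are increases in severity of substance use and/or signs of potentially medically dangerous withdrawal symptoms at study visits".

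The contact schedules differ by design:

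- Intervention participants start treatment at the randomization visit and "have a total of six intervention sessions over a total of eight weeks" (Assessment visits). Afterwards "participants will be allowed to attend up to 6 booster sessions", at any time before the 6-month assessment.
- For controls, "Control participants will also do timeline follow-back at their randomization visit", and "Control participants will also be invited to the clinic for urinalysis and timeline follow-back approximately 5-weeks post-randomization" (footnote to Table 2, List of Measures).
- The mandatory visits named for the completion certificate show the same contrast: "intervention: all assessments and all six intervention sessions; control: all assessments and midpoint urinalysis".
- Both arms have the post-treatment and 6-month assessments (about 10 and 22 weeks after randomization), a Wisepill check-in, and reminder calls before follow-ups.

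**The concern.** A by-arm AE rate can be read as a comparison of harm only if both arms had a similar chance of having events noticed. Here one arm is seen more often, and the extra contacts are ones where trouble is likely to be mentioned: Sessions 3 to 6 open with a check on substance use and adherence, and boosters are meant for participants having difficulties. Between weeks 10 and 22 a control has no scheduled contact apart from the reminder calls before the 6-month visit.

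Two errors could follow. The DSMB, which has no pre-specified stopping rule and must weigh risk against benefit by judgment, could see an excess that reflects frequency of contact. Events in controls could also be learned late or not at all. That matters for serious events too, because the reporting clock starts only when the team becomes aware.

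**Working it through.** The documents give no contact ratio, AE rate or AE calculation, so there is no stated figure to reproduce.

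**Step 1. Scheduled contacts from randomization on.**

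- Intervention: 6 sessions (the first at the randomization visit) + 2 assessments = 8.
- Control: randomization visit + week-5 visit + 2 assessments = 4.

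| Count | Intervention v control | Ratio | With all 6 boosters |
|---|---|---|---|
| Visits | 8 v 4 | 2.0 | 14 v 4 = 3.5 |
| Visits + Wisepill check-in | 9 v 5 | 1.8 | 15 v 5 = 3.0 |
| Visits + 4 reminder calls | 12 v 8 | 1.5 | 18 v 8 = 2.25 |

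**Step 2. Apparent ratio if true harm is equal.** Suppose AEs occur uniformly over the 22 weeks and an event is recorded only if a contact falls within w weeks after it. For contacts at times t(1) < t(2) < …, the weeks covered are the sum of min(w, t(j) − t(j−1)), and the apparent ratio is intervention weeks over control weeks. The window w is an assumption. I place control contacts at weeks 0, 5, 10 and 22; sessions evenly over weeks 0 to 8 (1.6 weeks apart), then 10 and 22; and boosters, if any, evenly over weeks 12 to 20.

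| w | Intervention weeks | Control weeks | Ratio | Ratio with 6 boosters |
|---|---|---|---|---|
| 1 | 5×1 + 1 + 1 = 7 | 1 + 1 + 1 = 3 | 2.33 | 13/3 = 4.33 |
| 2 | 8 + 2 + 2 = 12 | 2 + 2 + 2 = 6 | 2.00 | 22/6 = 3.67 |
| 4 | 8 + 2 + 4 = 14 | 4 + 4 + 4 = 12 | 1.17 | 22/12 = 1.83 |
| 6 | 8 + 2 + 6 = 16 | 5 + 5 + 6 = 16 | 1.00 | 22/16 = 1.375 |
| 12 or more | 22 | 22 | 1.00 | 1.00 |

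Adding the shared check-in at week 4 (midway between baseline at week −2 and post-treatment at week 10) gives 1.90, 1.71 and 1.08 for w = 1, 2 and 4 without boosters, and 3.40, 3.14 and 1.69 with six. The ethics chapter describes the sessions as taking 6 to 8 weeks. With a 6-week span, w = 2 gives (6 + 2 + 2)/6 = 1.67, and the other rows without boosters do not change.

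**Step 3. A second model.** Suppose a lasting event is found with probability q at each contact, so that over k contacts the chance of detection is 1 − (1 − q)^k. For k = 4, 8 and 14:

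- q = 0.05: 0.185, 0.337 and 0.512; ratio 1.81, or 2.76 with boosters.
- q = 0.25: 0.684, 0.900 and 0.982; ratio 1.32, or 1.44 with boosters.
- q = 0.5: ratio 1.06, or 1.07 with boosters.

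The ratio is never below 1.0 in either model, so any distortion from contact runs in one direction.

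**Step 4. Do the planned breakdowns remove it?** Splitting by treatment phase does not: the extra sessions fall in the treatment phase and the boosters in follow-up. Severity, type and relatedness describe events already found and cannot recover control events that were not. No field records the contact at which an event was learned.

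**Step 5. Effect of a common inquiry.** If the visits both arms attend each ask about the time since the last shared visit, each arm is covered for all 22 weeks and the ratio is 1.0, provided recall holds. Evenly spaced sessions would put Session 3 at 2 × 1.6 = week 3.2 rather than week 5. That moves the boundary between two recall periods but not the total covered.

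**The case against.** The protocol promises all staff extensive training in ascertaining AEs, and the absence of an AE form from a list of measures does not prove that nobody asks. Both arms complete depression, alcohol, drug-problem and resource-use measures, urinalysis and chart extraction at the major assessments. The follow-up treatment-utilization measure covers the whole interval since the last assessment. Worsening substance use in controls is therefore measured on a common schedule. The summaries are descriptive, with no between-arm test, in a 60-person trial of low-risk counselling, and they go to a board with biostatistical expertise that may request any analysis.

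Much of this stands, and it rules out three stronger readings:

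- A reader might infer that equal harm is bound to appear as excess harm. It is not: the result depends on recall and elicitation, which the protocol leaves open, and under long recall or high detection the ratio is 1.0.
- A reader might take 3.5 as the ratio of scheduled contacts. Boosters are optional, so 3.5 (and the 4.3 in Step 2) needs every intervention participant to attend all six.
- A reader might suppose that the by-arm AE table is the board's only quantitative safety information. The board also receives full reports on every serious event, and retention and reasons for dropout by arm.

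The objection does not remove the gap. Training staff does not give the two arms equal opportunity. No section says that questionnaire answers become AE records; the resource-use questionnaire is described as input to cost-effectiveness work. Neither chart-extraction description names hospital admissions, although the list under Sources of material gives only examples.

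One further objection shapes the remedy. The protocol names short-term negative affect during active treatment sessions as a foreseeable risk. By-arm rates limited to shared visits could take that very harm out of the board's main view.

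**Conclusion.** The concern holds as a possible bias in one direction, of uncertain size. Scheduled visits from randomization are about 2 to 1 (1.8 with the shared check-in), recording rests on staff awareness, and nothing in either document makes ascertainment comparable before numbers and rates are shown by arm. With equal true harm the illustrative apparent ratio is 1.0 to 2.3 without boosters and up to 4.3 with all six. These ranges rest on assumed recall windows, even spacing of visits and uniform timing of events; booster uptake is unknown. Mild, short-lived events are likely to be the most exposed. Events that reach staff regardless of visits are little affected. The point concerns how the safety tables are read, not the effectiveness analysis. It should be fixed because the correction is small and the plan, followed as written, can mislead in a known direction.

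**What to change.** 1. Add one standard question on AEs and hospital admissions, covering the time since the last shared visit, at the visits both arms attend: the mid-point urinalysis visit (Session 3 in the intervention arm), post-treatment and 6-month. Add it to the measures tables.
2. Record for each AE the contact at which it was learned: shared visit, session, booster or other.
3. State the denominator for AE rates.
4. Give the DSMB two by-arm tables side by side: rates from the common inquiry, for the like-for-like comparison, and all AEs from any source, with those learned only at sessions or boosters marked. The second table keeps distress arising in sessions in view.
5. Leave immediate reporting of serious events from any contact unchanged.

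The cost is a few minutes per visit, one REDCap field and one extra table. Recorded AEs in controls may rise. The 6-month inquiry relies on recall over about 12 weeks, so it makes the arms comparable without guaranteeing that every event in that interval is found.
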